We will enroll all primary care physicians and their eligible patients. Eligible patients include adults ≥ 18 years and < 85 years with a diagnosis of diabetes, hypertension, or hyperlipidemia; evidence of poor or worsening disease control (see Table 1); and evidence of medication non-adherence based on medication refill data. Disease control is evaluated using the most recent lab or blood pressure values in the electronic health record and is based on clinical guideline targets from the American Diabetes Association (ADA), the Eighth Joint National Committee (JNC 8) hypertension guidelines, and the American College of Cardiology/American Heart Association (ACC/AHA) cholesterol guidelines. Adherence is assessed using prescription claims data. HVMA prescription data are available with a one-month lag. For each medication used to treat any one of the targeted conditions, the proportion of days covered (PDC) is calculated as the number of days of medication that a patient filled between the first fill date and the randomization date divided by the number of days in that same period (up to a maximum of 365 days). We consider drugs that are chemically related and not intended for use in combination to be interchangeable (e.g., two different statins). We average the PDC for all medications used to treat a single condition (e.g., all oral hypoglycemics) and then calculate an overall average adherence for all of the conditions that a patient had at the time of their identification.

TABLE 1. Definitions of poor and worsening disease control

Condition	Age (years)	Poor control	Worsening control
Diabetes	...	Latest HbA1c > 8	Latest HbA1C $7.5 \leq \text{to} \leq 8$, and previous HbA1C 1% lower
Hypertension	≥ 60	Latest BP $> 150/90$	Latest BP $140/80 \leq \text{to} \leq 150/90$, and previous BP 20 mmHg lower
	< 60	Latest BP $> 140/90$	Latest BP $130/80 \leq \text{to} \leq 140/90$, and previous systolic or diastolic BP 20 mmHg lower
Hyperlipidemia	...	Diagnoses of ASCVD	...
	40-75	Type 1 or 2 diabetes and use of glucose lowering agent	...
	40-79	ASCVD risk $> 7.5\%$...
	...	LDL $> 190 \text{ mg/dl}$	Latest LDL $175 \leq \text{to} \leq 190$, and previous LDL 30 mg/dl lower

...= N/A; Abbreviations: HbA1c, glycosylated hemoglobin; BP, blood pressure; ASCVD, atherosclerotic

cardiovascular disease; LDL, low-density lipoprotein

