To identify individuals who would benefit most from the intervention, a patient is defined as being non-adherent if they (1) have been less than 80% adherent to the specific class of medications used to treat the condition(s) for which they were being identified as being poorly controlled and (2) if their “average of averages” PDC for all eligible study drugs is less than 80%. For example, patients with poorly

controlled diabetes who are non-adherent to their diabetes medications but adherent to their statins and antihypertensives, would only be eligible if their average adherence across all 3 conditions is less than 80%. Patients are excluded if, prior to randomization, they have less than 6 months of continuous enrollment in the health plan (to allow adequate assessment of eligibility), are < 18 or > 85 years of age, or have no available telephone contact information, which would preclude contact for enrollment and delivery of the intervention.

Study procedures

Once identified, PCPs of potentially eligible intervention group patients will be sent a secure message using the electronic health record to ask permission to include their patient(s) in the study. If a physician does not explicitly respond to approve or disapprove of the identified patient(s) to participate in the study within 5 days, they are sent a reminder message; one day later, their patients will automatically be opted in to the study.

Patients approved for enrollment in the study are sent a letter informing them about the study along with a simple, one compartment per day, pillbox that allows for the storage of one week of medication. Patients are then contacted by telephone to schedule a phone consultation with the clinical pharmacist. At this time, they are also administered the Patient Activation Measure (PAM), a questionnaire to assess the knowledge, skills, and confidence to manage one's health and health care. The PAM is subsequently used to tailor the intervention for that individual patient.

Intervention

The central component of the multi-faceted intervention is an individually-tailored telephone consultation conducted by a clinical pharmacist who is part of the Harvard Vanguard care team. The

clinical pharmacists work at multiple sites; in order to reduce the chances of contamination, they are restricted to providing clinical services only at other intervention sites during the time period of this study.

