The independent variable of interest is exposure to the pharmacist intervention. We will measure several variables to assess the degree of balance between patients and physicians randomized to intervention versus control, to adjust for chance imbalances, and to assess whether the efficacy of the intervention is modified by particular patient characteristics. Patient demographic characteristics and major comorbid conditions, as identified based on EHR data, will be included as independent variables

HVMA currently has an existing clinical pharmacy program. These clinical pharmacists already work collaboratively with the primary care physicians in the clinics to provide patient education and advice around medication management. Primary care physicians can currently refer patients to the clinical pharmacist using an electronic referral in the electronic health record.

Final analysis plan

Sample size considerations

Our study should be sufficiently powered to detect small, clinically meaningful changes in the primary outcome. We powered the study to detect a 2.5% mean change in adherence between the intervention and control groups, assuming a standard deviation of 0.25 (a conservative assumption), clustering at the practice level with a design effect of 1.10, and a 15% non-differential loss to follow-up rate. We assumed that 95% of potentially eligible intervention patients would be approved for study inclusion by their PCPs and that 50% of these patients would agree to a pharmacist consultation. With these assumptions, we estimated that we would need a total sample size of 4000 eligible patients to provide more than 80% power to detect differences in our primary study outcome of medication adherence. In other words, if those patients receiving the intervention demonstrate a 4.6% improvement in adherence, we will still have more than 80% power to detect an improvement of 2.5% in the overall sample. We also have substantial power to detect improvements in disease control, assuming a rate of controlled disease of 30% based on our pilot data.

Outcome Measures

Primary outcome - Adherence

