The trial's primary outcome is medication adherence assessed at 12 months after randomization. Medication adherence will be assessed using prescription claims data and measured as the mean PDC over the 12 months after randomization using the "average of averages" approach used for study eligibility. Adherence will be measured only for medications that qualified a patient for inclusion in the study and follow-up will begin at the point of randomization

Secondary outcomes

The secondary outcomes for the study include disease control and rates of healthcare utilization.

Disease control will be measured as the following two different outcomes: (1) the proportion of patients achieving good disease control for all of their eligible conditions and (2) the proportion of patients achieving good disease control for at least one of their eligible conditions. Because disease control will be evaluated using biometrics that are collected during routine care rather than at study-prescribed intervals, we will use those values that are closest to each patient's 12-month end of follow-up period up to a maximum of 15 months after randomization

Rates of healthcare utilization will also be measured using administrative claims data and will include all-cause emergency room visits, physician office visits, and hospitalizations during follow-up

Statistical analyses

We will report the means and frequencies of pre-randomization variables separately for intervention and control subjects. Comparisons of these values will be performed using t-tests and chi square tests and their non-parametric analogs, as appropriate. The outcomes will be evaluated using intention-to-treat principles among all randomized patients. In the primary analysis, the outcomes will be compared using generalized estimating equations with an identity link function and normally distributed errors to account

for the clustering of subjects within practice sites. Our primary models will also adjust for the block-randomized design. If there are differences in baseline characteristics between study groups that are believed to be confounders of the intervention–outcome association, we will repeat our analyses after adjusting for these covariates.

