A similar approach will be taken for the analysis of the secondary outcomes, except using logit link functions with binary errors and log link functions with Poisson errors, as appropriate. If more than 10% of subjects have missing outcome data, we will repeat our analyses using the latest post-randomization lab values available and using multiple imputation.

Several additional analyses will also be conducted. First, we will assess the correlation between calculated adherence based on insurer claims, self-reported adherence, and pharmacy transaction records (for patients filling prescriptions at Harvard Vanguard pharmacies). Second, we will use Markov modeling to assess the long-term impact of the intervention on cost, quality-adjusted survival, and cost-effectiveness of the intervention

Potential confounders

We will measure several variables to assess the degree of balance between patients and physicians randomized to intervention versus control, to adjust for chance imbalances, and to assess whether the efficacy of the intervention is modified by particular patient characteristics such as baseline patient demographic characteristics, major comorbid conditions, medication use, and healthcare utilization as identified based on claims and EHR data.

Summary of changes to the analysis plan

Detailed sample size calculations are now provided which was not included in the original plan. The primary and secondary outcomes are now clarified along with the specific analytic strategy for these outcomes.

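### The primary GEE adjusts only for block and omits baseline PDC, which the trial already computes for every patient to decide eligibility

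*Combined protocol and SAP*

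**What the plan says.** The primary outcome is mean PDC over the 12 months after randomisation, averaged within and then across conditions as for eligibility (Final analysis plan, Primary outcome - Adherence). The primary model is a GEE with identity link and normal errors, clustered by practice site. One adjustment is named, in both Statistical analyses (Final analysis plan) and Analytic plan (Final protocol): "Our primary models will also adjust for the block-randomized design". Under Study design and randomization, the blocks are formed from site size and whether site pharmacists counsel patients directly.

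Other covariates are conditional: "If there are differences in baseline characteristics between study groups that are believed to be confounders of the" relation between intervention and outcome, the analyses are repeated with them. For the baseline comparison itself, "Comparisons of these values will be performed using t-tests and chi square tests and their non-parametric analogs, as appropriate". Potential confounders adds that variables will be measured "to adjust for chance imbalances, and to assess whether the efficacy of the intervention is modified by particular patient characteristics", and its examples include medication use. It names neither PDC nor the primary model.

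A baseline PDC exists for every patient. Final protocol, Subjects, computes PDC per drug from first fill to randomisation (at most 365 days), averages it within condition, and then says the team will "calculate an overall average adherence for all of the conditions that a patient had at the time of their identification". Entry requires that the average "PDC for all eligible study drugs is less than 80" per cent.

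The two measures differ in scope. Eligibility uses all eligible study drugs, whereas for the outcome "Adherence will be measured only for medications that qualified a patient for inclusion in the study".

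**The concern.** A pre-randomisation value of the outcome is usually among the strongest predictors of that outcome. Here it is already held for everyone, yet the primary model leaves it out. Two things are at stake.

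- **Precision.** At the plan's own inputs, power at 4000 patients sits at the edge of the stated claim of more than 80%, so even a modest baseline-outcome correlation is useful.
- **Chance imbalance.** Only 14 sites were randomised. A difference between arms in mean baseline PDC passes into the block-adjusted estimate in proportion to the baseline-outcome slope. Whether anything is done about it rests on a judgement made after the baseline data are seen. The only comparison methods named to inform that judgement are tests for which no allowance for clustering is stated.

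**Working it through.** **Inputs.** From Sample size considerations: difference 0.025, SD 0.25, "clustering at the practice level with a design effect of 1.10", loss 15%, N = 4000. From Study design and randomization: 14 sites, 1:1. Assumed because the documents do not state them: two-sided 5%, and the correlation r between baseline and 12-month PDC. The SEs ignore block stratification.

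**1. The plan's sample size.** n per arm = 2 × (1.96 + 0.84)² × 0.25² / 0.025² = 1570 (unrounded quantiles). Total 3140; × 1.10 = 3454; / 0.85 = 4064. This is 1.6% above 4000, so the stated size reproduces without any baseline covariate.

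**2. Power at 4000, block only.** n per arm followed = 4000 × 0.85 / 2 = 1700. SE = √(2 × 0.25² × 1.10 / 1700) = 0.00899. Power = Φ(0.025/0.00899 − 1.96) = 79.4%.

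**3. Power with baseline PDC.** The SE is multiplied by √(1 − r²), taking the same correlation within and between sites. The equivalent enrolment without adjustment is 4000/(1 − r²).

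| r (assumed) | Power at 4000 | Equivalent N |
|---|---|---|
| 0 | 79.4% | 4000 |
| 0.2 | 81.0% | 4167 |
| 0.3 | 83.0% | 4396 |
| 0.5 | 89.4% | 5333 |

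Power reaches 80% at r = 0.125. If baseline PDC explains only within-site variation, power is 82.7% at r = 0.3 and 88.5% at r = 0.5.

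**4. Few clusters.** With a t reference on 12 degrees of freedom (14 sites − 2) in place of the normal, power is 72.3% unadjusted, 76.3% at r = 0.3, 79.5% at r = 0.4 and 83.8% at r = 0.5.

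**5. Chance imbalance at baseline.** SE of the between-arm difference in baseline PDC = √(2 × SD² × 1.10 / 2000).

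- SD 0.25 (assumed equal to the outcome SD): 0.83 points.
- SD 0.20 (assumed, if the 80% cap narrows the spread): 0.66 points.
- A one-SE imbalance carries slope × SE into the effect estimate: from 0.2 × 0.66 = 0.13 to 0.5 × 0.83 = 0.41 points.

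**6. Patient-level baseline tests.** A nominal 5% test that ignores clustering has size 2 × (1 − Φ(1.96/√1.10)) = 6.2%.

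**7. Dependence on the design effect.** The plan's 1.10 implies an ICC of 0.10 / (4000/14 − 1) = 0.00035. Suppose instead that it were 0.01 (assumed).

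- Baseline: design effect 1 + 284.7 × 0.01 = 3.85. The SE of the baseline difference is 1.55 points (SD 0.25), 0.31 to 0.78 points carry over, and the test size is 32%.
- Outcome: with 243 followed per site, the design effect is 3.42. Power is 35% unadjusted and 36% to 44% for r from 0.2 to 0.5.

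**The case against.** The strongest reply is that the planned analysis is valid and this is an optional gain in efficiency. Its points are these.

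- **The power gap is a matter of rounding.** At the 4076 patients given in the Final protocol's Background, the same formula gives 80.1% with no covariate. This is correct, and the stated power should not be said to depend on the fix. The plan does, however, tie its claim to 4000, and the margin is negligible at either figure.
- **The gain is unknown.** No correlation is given. The 80% cap and the varying look-back window may lower it, and at r = 0.2 the gain is 1.6 points. This stands. With 12 degrees of freedom, r = 0.125 would not reach 80%; slightly more than 0.4 would be needed. Adjustment still improves precision under either reference.
- **Imbalance is not an extra error.** The 0.13 to 0.41 points are part of the unadjusted estimate's 0.90-point SE, and blocking on site features may reduce them. This also stands: it is another view of the same lost precision.
- **Adjustment is already provided for.** The repeat analysis and the mention of medication use could take in prior adherence, and no significance threshold is set as the trigger. But neither names PDC or changes the primary estimate, and the choice is still made after baseline data are seen.
- **The ICC of 0.01 lies well outside the plan.** Agreed. It marks where the gains stop holding and is not a forecast.

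**Conclusion.** The concern holds. Block is the only covariate named for the primary GEE, although an average-of-averages PDC is computed before randomisation for every patient. The block-adjusted estimate is unbiased in expectation and remains a valid primary analysis; what is lost is precision and protection against chance imbalance. At the plan's inputs, adjustment would raise power from 79.4% to between 81.0% and 89.4% for correlations of 0.2 to 0.5, with the lower end plausible given the eligibility cap. This rests on a two-sided 5% level, an assumed correlation, a normal reference and the plan's design effect of 1.10. If clustering were much stronger, power would be low with or without the covariate. The change is recommended because it costs little, not because the trial fails without it.

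**What to change.** Before outcome data are seen, amend Statistical analyses as follows.

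1. Name baseline average-of-averages PDC as a fixed covariate in the primary GEE alongside block, whatever the observed balance. Compute it for the same qualifying medications as the outcome, over the existing pre-randomisation window. Under the identity link the target difference in mean PDC is unchanged.
2. Describe baseline balance with standardised differences in place of patient-level tests.
3. Label any further covariate-adjusted model as supportive.

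The cost is SAP wording and a recomputation of baseline PDC from the prescription claims already used for eligibility. No new data are needed.

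### The main utilization models fix only the randomization block as a covariate and leave baseline utilization to a conditional repeat analysis, so the headline rate ratios are less precise than they could cheaply be

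*Combined protocol and SAP*

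**What the plan says.** The Final analysis plan (Statistical analyses) sets out a GEE for the primary outcome that accounts for clustering by practice site, and adds: "Our primary models will also adjust for the block-randomized design". For the remaining endpoints it states: "A similar approach will be taken for the analysis of the secondary outcomes". Only the link and the error distribution change; for counts these are a log link and Poisson errors. The Final protocol (Analytic plan) ties the log-link Poisson model to healthcare utilization. No other covariate is fixed in advance for these models.

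Other covariates come in by a conditional route: "If there are differences in baseline characteristics between study groups that are believed to be confounders of the intervention–outcome association, we will repeat our analyses" with those covariates added. The section on potential confounders lists what will be measured at baseline, including "medication use, and healthcare utilization as identified based on claims and EHR data". It gives the purposes as checking balance and "to adjust for chance imbalances, and to assess whether the efficacy of the intervention is modified by particular patient characteristics".

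Two further facts bear on the point. The outcome and the baseline measure share a source: "Rates of healthcare utilization will also be measured using administrative claims data". And the Final protocol (Subjects) excludes patients if, before randomization, "they have less than 6 months of continuous enrollment in the health plan". Every patient therefore has a common look-back of at least 6 months.

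**The concern.** How often a patient used a service before randomization usually predicts how often the patient uses it afterwards. Leaving that count out of the main model leaves explainable variation in the standard error of the rate ratio. The loss occurs even when the arms are perfectly balanced, so a repeat analysis triggered by imbalance does not recover it in the headline estimate.

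The trigger is a weakness of its own. Whether an adjusted result exists depends on baseline differences seen in the data and on a judgement that they confound. The plan gives no threshold, no fixed covariate list, no look-back or functional form, and no statement of which result leads if the two disagree.

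The design makes this relevant. Only 14 sites were randomized, and the blocks reflect site size and on-site pharmacist counseling, not a site's usual visit rate. At stake is the chance of detecting a real change in utilization, and a clear reading of the result if adjusted and block-only models differ.

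**Working it through.** **The plan's own figure.** The documents state no power for utilization. Their only sample-size figure concerns adherence, and it reproduces, assuming a two-sided 5% level: per arm 2 × 0.25² × (1.96 + 0.8416)² / 0.025² = 1,570, so 3,140 in total; × 1.10 = 3,454; / 0.85 = about 4,063, against 4,000 stated. The present point does not touch it.

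**Inputs from the documents.** 14 sites; 4 blocks, 1:1 allocation; 4,000 patients with 15% loss, so 4,000 × 0.85 = 3,400 analysed; at least 6 months of prior enrollment.

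**Inputs that must be assumed.** Event rates, overdispersion, between-site variation in utilization, and the baseline-to-follow-up correlation ρ. The adherence design effect of 1.10 does not transfer to visit counts.

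**Formula.** In a normal approximation, adjusting for a baseline value multiplies the variance by 1 − ρ². For an endpoint with 80% unadjusted power, adjusted power = Φ[(0.8416 + 1.96)/√(1 − ρ²) − 1.96].

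| Assumed ρ | Variance × | Power |
|---|---|---|
| 0.3 | 0.91 | 83.6% |
| 0.4 | 0.84 | 86.4% |
| 0.5 | 0.75 | 89.9% |
| 0.6 | 0.64 | 93.8% |

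The 80% is only a reference point.

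**Simulation.** Two simulations of Poisson log-link models compared block only with block plus log(1 + baseline count), using 14 sites of about 243 patients and assumed blocks of 4, 4, 4 and 2 sites. Simulation A used a capped 6-month baseline count, 1,500 replicates, and annual rates of 6 (office), 0.5 (emergency) and 0.15 (hospitalization). Simulation B used an uncapped baseline count with the same mean as follow-up (in effect a full year), 300 replicates, annual rates of 6, 0.4 and 0.15, and 70% persistence of patient-level use. Entries are the variance of the adjusted over the block-only log rate ratio, by between-site SD of the log rate.

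| Service | A: SD 0 / 0.05 / 0.15 | B: SD 0.03 / 0.1 / 0.2 |
|---|---|---|
| Office, ρ about 0.5 (A) or 0.6 (B) | 0.69 / 0.50 / 0.24 | 0.41 / 0.32 / 0.24 |
| Office, ρ about 0.37 (A) | 0.86 / 0.67 / 0.35 | not run |
| Emergency, ρ about 0.34 | 0.87 / 0.84 / 0.66 | 0.87 / 0.70 / 0.58 |
| Hospitalization, ρ 0.16–0.27 (A) or about 0.17 (B) | 0.86–0.98 over all settings | 0.98 / 0.92 / 0.78 |

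From an 80% reference with no site variation, A gives 86% to 92% for office visits and 85% for emergency visits. For hospitalizations it gives 81% to 86% over its settings. Both simulations favour adjustment somewhat: neither specifies any drift in a site's usual rate between periods, and B's look-back is longer than the one the plan guarantees.

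**Functional form.** In A, an uncapped term plus an any-use indicator raised the variance for hospitalizations (ratio 1.02 to 1.24). The form must therefore be fixed, not left open.

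**The case against.** The strongest reply is that the plan already provides for this. It commits to repeating the analyses with covariates when baseline differences are thought to confound, it carries that approach to the secondary outcomes, and it names healthcare utilization among the variables measured so that chance imbalance can be adjusted for. This stands. A reader might infer that baseline utilization is never adjusted for; the documents do not support that. What they show is adjustment that is conditional, secondary and without a criterion.

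A reader might also infer that, with 14 sites, a pre-existing site difference could pass for an intervention effect and bias the rate ratio. With 7 sites per arm (assumed), the arm difference in site means has an SD of √(2/7) = 0.53 site SDs. It exceeds half a site SD with probability 35% if blocking explains none of the between-site variance, and 19% if it explains half. But sites were randomized and the GEE accounts for clustering by site. Such imbalance is random error that the standard error is meant to cover. Counting it as bias as well as lost precision counts one thing twice. Whether the interval is reliable with 14 clusters is a separate question, which this change does not settle.

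Third, the largest gains should not be relied on. At an assumed site SD of 0.15, site variation alone gives a standard error of 0.15 × √(2/7) = 0.080. Unadjusted 80% power then needs a log rate ratio of at least 2.80 × 0.080 = 0.225, about a 20% reduction. With 0.95 × 0.50 = 47.5% of intervention patients consulted and no effect in the rest, that is 20/47.5, about a 42% reduction among those consulted. Nothing in the documents supports that SD or that effect.

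**Conclusion.** The point holds as one of precision and pre-specification. The block-adjusted rate ratios are valid, but the main models omit a predictor that the plan already measures, and the only route to using it depends on the data. The documents cannot fix the size. With an assumed correlation of 0.3 to 0.5, an endpoint at 80% power would move to about 84% to 90%. The gain is likely useful for office and emergency visits and small for hospitalizations unless sites vary widely. This rests on prior use predicting later use and on the 6-month enrollment covering medical as well as pharmacy claims, which the text does not state outright. The documents do not support a charge of bias or of no provision for adjustment. The primary outcome and its sample size are unaffected, so this is an inexpensive improvement to secondary analyses, not a defect in the trial's main conclusion.

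**What to change.** In the secondary-outcome sentence of the Final analysis plan (Statistical analyses), and in the matching sentence of the Final protocol (Analytic plan), add wording such as:

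> Each main utilization model will include, besides the randomization block, the patient's count of the same service (emergency visits, office visits or hospitalizations) in the 6 months before randomization, entered as log(1 + count) and capped at the pooled 99th percentile of the baseline count. The cap will be fixed before outcome data are seen by arm. The adjustment applies whatever baseline differences are observed. The block-only model will be reported as a supporting analysis.

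The percentile is an example; what matters is that a value is set in advance.

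The cost is one sentence and one covariate per model, from claims data already planned for collection. The drawbacks are modest: the adjusted rate ratio is conditional on prior use, one more parameter is estimated with 14 clusters, and little is gained for hospitalizations.
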